### **4.4. End of Study Definition**

A participant is considered to have completed the study if the participant has completed all periods of the study, including the last scheduled procedure shown in the SoA.

The end of the study is defined as the date of the last visit of the last participant in the study or last scheduled procedure shown in the SoA for the last participant in the study.

## 5. Study Population

Prospective approval of protocol deviations to recruitment and enrollment criteria, also known as protocol waivers or exemptions, is not permitted.

### 5.1. Inclusion Criteria

Participants are eligible to be included in the study only if all of the following criteria apply:

#### Age

1. Participants must be  $\geq 12$  years of age inclusive, at the time of signing the informed consent/assent.

#### Type of Participant and Disease Characteristics

2. Participants who are self-reported race other than White, including but not limited to persons who self-identify as Black or African American, American Indian or Alaska Native, Asian, Native Hawaiian, or Other Pacific Islander.
3. Participants who are Fitzpatrick phototype IV-VI (Section 8.1.15).
4. Have chronic AD (according to American Academy of Dermatology Consensus Criteria; Eichenfield et al. 2014; Appendix 7, Section 10.7) that has been present for  $\geq 1$  year before screening visit.
5. Have EASI  $\geq 16$  at the baseline visit.
6. Have Investigator's Global Assessment (IGA) score  $\geq 3$  (scale of 0 to 4) at the baseline visit.
7. Have  $\geq 10\%$  BSA of AD involvement at the baseline visit.
8. Have a history of inadequate response to treatment with topical medications; or determination that topical treatments are otherwise medically inadvisable.

#### Weight

9. For adolescent participants, body weight  $\geq 40$  kg at baseline.

#### Sex and Contraceptive/Barrier Requirements

10. Male and/or female
  - a. No male contraception is required except in compliance with specific local government study requirements.
  - b. Female participants of child-bearing potential must agree to remain abstinent (refrain from heterosexual intercourse) or use a highly effective contraceptive method during the treatment period and for at least 18 weeks after the last dose of study drug. Women not of child-bearing potential (WNOCBP) may participate without any contraception requirements. For definitions of women of child-bearing potential (WOCBP) and WNOCBP, see Section 10.4, Appendix 4.

Contraceptive use by participants should be consistent with local regulations regarding the methods of contraception for those participating in clinical studies. For the contraception requirements of this protocol, see Section 10.4, Appendix 4.

## Informed Consent

### 11. Informed consent/assent

- a. For adult participants: capable of giving signed informed consent as described in Appendix 1, which includes compliance with the requirements and restrictions listed in the ICF and in this protocol.
- b. For adolescent participants: a parent or legal guardian must be able to read, understand, and give documented informed consent for a child to participate in this study as described in Section 10.1.3, which includes compliance with the requirements and restrictions listed in the ICF and in this protocol.

NOTE: Adolescents reaching the age of majority while on study must provide consent to continue participation in the study.

## Other

12. Are willing and able to comply with all clinic visits and study-related procedures and questionnaires.

## 5.2. Exclusion Criteria

Participants are excluded from the study if any of the following criteria apply:

### Medical Conditions

13. History of human immunodeficiency virus (HIV) infection or positive HIV serology at screening.
14. Have a current infection or chronic infection with hepatitis B virus (HBV) at screening, that is, positive for hepatitis B surface antigen (HBsAg) and/or polymerase chain reaction positive for HBV DNA (Section 8.2.3).
15. Have a current infection with hepatitis C virus (HCV) at screening, that is, positive for HCV RNA (Section 8.2.4).
16. Have an uncontrolled chronic disease that might require multiple intermittent uses of oral corticosteroids at screening (as defined by the investigator).
17. Have uncontrolled asthma that
  - a. might require bursts of oral or systemic corticosteroids, or
  - b. required the following due to  $\geq 1$  exacerbations within 12 months before baseline
    - i. systemic (oral and/or parenteral) corticosteroid treatment, or
    - ii. hospitalization for  $>24$  hours.
18. Have known liver cirrhosis and/or chronic hepatitis of any etiology.
19. History of malignancy, including mycosis fungoides or cutaneous T-cell lymphoma, within 5 years before the screening, except completely treated in situ carcinoma of the cervix of completely treated and resolved non-metastatic squamous or basal cell carcinoma of the skin with no evidence of recurrence in the past 12 weeks.
20. Are diagnosed with active endoparasitic infections or at high risk of these infections.
21. Have a known or suspected history of immunosuppression, including history of invasive opportunistic infections (e.g., tuberculosis, histoplasmosis, listeriosis,

- coccidioidomycosis, pneumocystosis, and aspergillosis) despite infection resolution; or unusually frequent, recurrent, or prolonged infections, per the investigator's judgment.
22. Have presence of skin comorbidities that may interfere with study assessments.
  23. Have a severe concomitant illness(es) that in the investigator's judgment would adversely affect the participant's participation in the study.
  24. Have any other medical or psychological condition that in the opinion of the investigator may suggest a new and/or insufficiently understood disease, may present an unreasonable risk to the study participant because of his/her participation in this clinical trial, may make participant's participation unreliable, or may interfere with study assessments.
  25. Have had any of the following types of infection within 3 months of screening or develop any of these infections during screening:
    - a. Serious (requiring hospitalization, and/or intravenous or equivalent oral antibiotic treatment)
    - b. Opportunistic (as defined in Winthrop et al. 2015, see Section 10.9, Appendix 9)  
NOTE: Herpes zoster is considered active and ongoing until all vesicles are dry and crusted over.
    - c. Chronic (duration of symptoms, signs, and/or treatment of 6 weeks or longer)
    - d. Recurring (including, but not limited to recurring cellulitis, chronic osteomyelitis)  
NOTE: Participants with only recurrent, mild, and uncomplicated orolabial and/or genital herpes may be discussed with the sponsor's medical monitor to determine whether the participants meet this exclusion criterion.
  26. Have an active or acute infection requiring treatment with systemic antibiotics, antivirals, antiparasitics, antiprotozoals, or antifungals within 2 weeks before the baseline visit (baseline; Visit 2), or superficial skin infections within 1 week before the baseline visit.  
NOTE:  
Participants may be rescreened after infections resolves.  
Participants who have an upper respiratory infection, a vaginal candida infection, or an oral candida infection and who are being treated only symptomatically and not requiring systemic anti-infectives may be considered for enrollment if other study eligibility criteria are met. Enrollment of participants with other uncomplicated local infections should be discussed with the sponsor's designated medical monitor.

### **Prior/Concomitant Therapy**

27. Prior treatment with tralokinumab.
28. Prior treatment with dupilumab.
29. Treatment with topical agents: corticosteroids, calcineurin inhibitors, JAK inhibitors, or phosphodiesterase-4 inhibitors, such as crisaborole within 2 weeks prior to baseline visit.
30. Treatment with any of the following agents within 4 weeks prior to the baseline visit:
  - a. systemic immunosuppressive or immunomodulating drugs (e.g., systemic corticosteroids, cyclosporine, mycophenolate mofetil, IFN-gamma, azathioprine, methotrexate, and other immunosuppressants)
  - b. small molecules (e.g. JAK inhibitors)

- c. phototherapy and photochemotherapy for AD.
31. Have regularly used (more than 2 visits per week) a tanning booth or parlor within 4 weeks of the screening visit (Visit 1).
  32. Are currently receiving build-up dosing of allergen immunotherapy (allergy shots).
  33. Treatment with B-cell-depleting biologics, including rituximab, within 6 months prior to the baseline visit.
  34. Use of prescription moisturizers within 7 days of the baseline visit.
  35. Have received any live attenuated vaccine within less than 4 weeks of the baseline visit, or intend to receive a live attenuated vaccine during the study, or within 4 weeks after receiving the last dose of study intervention.

NOTE: The following are not considered live vaccines: RNA vaccines, vaccines with inactive viral elements, and/or nonreplicating viral vector vaccines.

36. Have received a Bacillus Calmette-Guerin (BCG) vaccination or treatment within less than 4 weeks before the baseline visit, or intend to receive BCG vaccination or treatment during the study.
37. Use of cannabis or cannabinoids for the treatment of pruritus, pain, and/or AD.

#### **Diagnostic Assessments**

38. In the opinion of the investigator, have any clinically significant laboratory results from the chemistry or hematology tests obtained at the screening visit (Visit 1).

#### **Prior/Concurrent Clinical Study Experience**

39. Are currently enrolled in any other clinical study involving an investigational product or any other type of medical research judged not to be scientifically or medically compatible with this study.
40. Treatment with an investigational drug within 8 weeks or within 5 half-lives (if known), whichever is longer prior to the baseline visit.
41. Have received a dose of lebrikizumab in any prior lebrikizumab clinical study.

#### **Other Exclusions**

42. Are Lilly employees, or are employees of any third-party involved in study who require exclusion of their employees.
43. Are investigator site personnel directly affiliated with this study and/or their immediate families. Immediate family is defined as a spouse, parent, child, or sibling, whether biological or legally adopted.
44. Are pregnant or breastfeeding or are planning to become pregnant or to breastfeed during the study.
45. Have a known hypersensitivity to any component of lebrikizumab.
46. Participant or caregiver who is unwilling to administer SC injections of study medication.

### **5.3. Lifestyle Considerations**

Not applicable.

## **5.4. Screen Failures**

A screen failure occurs when a participant who consents to participate in the clinical study is not subsequently enrolled in the study. A minimal set of screen failure information is required to ensure transparent reporting of screen failure participants to meet the Consolidated Standards of Reporting Trials publishing requirements and to respond to queries from regulatory authorities. Minimal information includes demography, screen failure details, eligibility criteria, and any SAE.

Individuals who do not meet the criteria for participation in this study (screen failure) may be rescreened as defined below. Rescreened participants should be assigned a new participant number for every screening or rescreening event.

### **5.4.1. Rescreening for Individuals Who Failed Screening**

#### **Informed consent for rescreenings**

Individuals who are to be rescreened must first sign a new ICF (Appendix 10, Section [10.1.3](#)). Such individuals will be assigned a new participant number.

#### **Rescreening after failure to meet study entry criteria**

An individual who does not meet the criteria for participation in this study for any reason may be rescreened **one time**.

When rescreening, all of the screening tests and procedures should be repeated.

## **5.5. Criteria for Temporarily Delaying Enrollment/Administration of Study Intervention of a Participant**

Not applicable.

## 6. Study Intervention(s) and Concomitant Therapy

Study intervention is defined as any investigational intervention(s), marketed product(s), placebo, or medical device(s) intended to be administered to/used by a study participant according to the study protocol.

### 6.1. Study Intervention(s) Administered

Lebrikizumab drug product is provided as sterile liquids and contain no preservatives.

Intervention Name	Lebrikizumab
Dose Formulation	250 mg (125 mg/mL), 2 mL Solution
Dosage Level	
Loading Dose:  Week 0: 500 mg (2 injections of 250 mg)  Week 2: 500 mg (2 injections of 250 mg)
 
Post-loading Dose:  Weeks 4-16: 250 mg SC Q2W (1 injection of 250 mg)  Responders at Week 16: 250 mg SC Q4W (1 injection of 250 mg) at W20  Inadequate responders at Week 16: 250 mg SC Q2W (1 injection of 250 mg) at W18, W20, and W22

Route of Administration	SC

Abbreviations: mg = milligram; mL = milliliter; SC = subcutaneously; Q2W = once every 2 weeks; Q4W = once every 4 weeks; W = week.

#### 6.1.1. Medical Devices

1. Lebrikizumab will be administered using a sterile prefilled syringe with needle safety device. Each prefilled syringe is intended for a single 2 mL dose (250 mg) administered subcutaneously device.
2. Instructions on how to use the device will be provided.
3. All PCs, including malfunction, use error, and inadequate labeling, shall be documented and reported by the investigator throughout the clinical investigation (see Section 8.2.2) and appropriately managed by the sponsor.

### 6.2. Preparation, Handling, Storage, and Accountability

1. The investigator or designee must confirm appropriate storage conditions have been maintained during transit for all study intervention received and any discrepancies are reported and resolved before use of the study intervention.
2. Only participants enrolled in the study may receive study intervention. Only authorized study personnel may supply, prepare, or administer study intervention, except for study intervention intended to be administered by the participant or caregiver. All study intervention must be stored in a secure, environmentally controlled, and monitored

(manual or automated) area in accordance with the labeled storage conditions with access limited to the investigator and authorized study personnel.

3. The investigator or authorized study personnel are responsible for study intervention accountability, reconciliation, and record maintenance (that is, receipt, reconciliation, and final disposition records).
4. Further guidance and information for the final disposition of unused study interventions are provided in the Study Reference Manual.

### **6.3. Measures to Minimize Bias: Randomization and Blinding**

In this open-label study, potential bias will be reduced by specifying treatment response ascertained from all eligible participants and safety reporting. Adherence to the study design requirements, including those specified in the SoA, is essential and required for study conduct.

The site will contact the interactive web-response system (IWRS), prior to the start of study intervention administration and at the primary endpoint for each eligible participant, to provide demographic information and IGA/EASI results, respectively.

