### 3. Objectives, Endpoints, and Estimands

Objectives	Endpoints
Primary	

 
To assess the effect of lebrikizumab 250 mg Q2W in reducing the signs and symptoms of AD in participants with moderate-to-severe AD and skin of color
 
	
 
Percentage of participants achieving EASI-75 (<math>\geq 75\%</math> reduction from baseline in EASI) at Week 16
 

Secondary	

 
To evaluate the effect of treatment with lebrikizumab in the signs and symptoms of AD and health outcome measures, in participants with moderate-to-severe AD and skin of color
 
	
 
Percentage of participants achieving EASI-75 at Week 24
 
Percentage of participants with an IGA score of 0 or 1 and a reduction <math>\geq 2</math> points from baseline to Weeks 16 and 24
 
Percentage change in EASI total from baseline to Weeks 16 and 24
 
Change in EASI total from baseline to Weeks 16 and 24
 
Percentage of participants achieving EASI 90 at Weeks 16 and 24
 
Percentage of participants with a Pruritus NRS of <math>\geq 4</math> points at baseline who achieve a 4-point reduction at Weeks 16 and 24
 
Percentage of participants with a Pruritus NRS <math>\geq 3</math> points at baseline who achieve at least 3-point reduction at Weeks 16 and 24
 
Percentage change in Pruritus NRS score from baseline to Weeks 16 and 24
 
Percentage of participants with a Sleep-Loss Scale score of <math>\geq 2</math> points at baseline who achieve a 2-point reduction at Weeks 16 and 24
 
Percentage change in Sleep-Loss Scale score from baseline to Weeks 16 and 24
 
Percentage of participants with a Skin Pain NRS of <math>\geq 4</math> points at baseline who achieve a 4-point reduction from baseline to Weeks 16 and 24
 
Change in POEM from baseline to Weeks 16 and 24
 
Change in DLQI from baseline to Weeks 16 and 24 for participants <math>\geq 16</math> years of age at baseline
 

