**Primary estimand**

The primary clinical question of interest is: What is the intervention effect in percentage of participants achieving at least 75% improvement from baseline in EASI-75 after 16 weeks of lebrikizumab 250 mg Q2W intervention in participants with skin of color and moderate-to-severe AD who remain on study treatment until Week 16.

The estimand is described by the following attributes:

Population: participants with skin of color and moderate-to-severe AD who met inclusion and exclusion criteria and who remained on study treatment until Week 16. Further details can be found in Section 5.

Endpoint: whether participants achieve at least 75% improvement from baseline in EASI at Week 16.

Intercurrent events: There are no intercurrent events for this population since participants who initiate rescue medication are discontinued from the study and hence study treatment. Therefore, participants who stay on study treatment through Week 16 will not have an intercurrent event such as initiating rescue medication or permanently discontinuing treatment. Further details on

study interventions and concomitant medications, including rescue treatments, can be found in Section [6.8.1](#).

Population-level summary: percentage of participants achieving EASI 75 response at Week 16.

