#### **6.8.5. Rescue Medicine for Atopic Dermatitis**

The goal of this Phase 3b study is to demonstrate the safety and efficacy of lebrikizumab for moderate-to-severe AD in participants with skin of color. To be consistent with real world practice, defined topical medications are allowed in this study (see Section 6.8.4). Rescue therapies may be needed if the participant experiences intolerable clinical worsening of symptoms. Escalation to high-potency topical TCS, topical JAKs, phototherapy, and/or systemic medications, including but not limited to corticosteroids, immunosuppressants, biologics, small molecules, etc., for the treatment of AD should only occur if participants do not respond adequately after at least 7 days of low- or mid-potency TCS, TCI, and/or topical PDE4 inhibitors. Any use of topical JAKs, phototherapy, and/or systemic medications will be considered Rescue Therapy. Use of high-potency TCS for more than 10 days is also considered Rescue Therapy. Participants that receive Rescue Therapy must be discontinued from the study (see Section 7.1). All rescue medication must be recorded in the CRF.

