### 7.1. Discontinuation of Study Intervention

When necessary, a participant may be permanently discontinued from study intervention. If so, the participant will remain in the study to complete procedures for an early discontinuation visit and post-treatment follow-up, if applicable, as shown in the SoA.

A participant should be permanently discontinued from study intervention if

- the participant becomes pregnant during the study
- in the opinion of the investigator, the participant should permanently discontinue the study intervention for safety reasons
- the participant develops a malignancy, except for successfully treated basal or squamous cell skin carcinoma
- the participant tests positive for HBV DNA (see Section 8.2.3)
- the participant tests positive for HCV RNA (Section 8.2.4)
- if the participant experiences a hepatic event or liver test abnormality as specified in the liver chemistry stopping criteria (see Section 7.1.1)
- the participant develops HIV infection
- the participant develops any infection that is opportunistic, such as active tuberculosis and other infections whose nature or course may suggest an immuno-compromised status
- the participant requires rescue medication treatment for symptoms of AD in the treatment period, and
- the participant has an AE or an SAE or a clinically significant change in a laboratory value that, in the opinion of the investigator, merits discontinuation of study intervention and appropriate measures being taken.

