### 8.1. Efficacy Assessments

#### 8.1.1. Eczema Area and Severity Index

The EASI is an investigator-reported, 20-item scale that evaluates 2 dimensions of AD: extent of disease at 4 body regions (head or neck, trunk, upper and lower extremities) and 4 clinical signs (erythema, induration or papulation, excoriation, and lichenification). The clinical signs are assessed for severity on a scale of 0 (absent) to 3 (severe).

The scores are added up for each of the 4 body regions. The assigned percentages of BSA for each section of the body are 10% for head or neck, 20% for upper extremities, 30% for trunk, and 40% for lower extremities, respectively. Each subtotal score is multiplied by the BSA represented by that region.

In addition, an area score of 0 to 6 is assigned for each body region, depending on the percentage of AD-affected skin in that area: 0 (none), 1 (1% to 9%), 2 (10% to 29%), 3 (30% to 49%), 4 (50% to 69%), 5 (70% to 89%), or 6 (90% to 100%). Each of the body area scores is multiplied by the area affected. The resulting EASI ranges from 0 to 72 points, with the highest score indicating worse severity of AD (Hanifin et al. 2001). The recall period of this scale is present time.

Assessors must be trained and certified by the sponsor prior to conducting this assessment. A single assessor should be assigned to each participant for as many visits as possible to avoid inter-assessor variability in scoring. The recall period of this assessment is present time.

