5.4.1 As Observed Analysis

The “as observed” strategy is used in so-called “observed cases” or “completers” analysis ubiquitous in the literature but is not one of the recommended strategies in the ICH E9(R1). For this analysis, only data from completers at the visit are relevant. All efficacy data will be

summarized using an “as observed” analysis and summaries based on observed data at each postbaseline visit will be provided.

5.4.2 *Last Observation Carried Forward*

In this analysis, all missing values will be imputed using last observation carried forward (LOCF). Baseline values will be used for imputation if there is no postbaseline observation.

5.4.3. *Markov chain Monte Carlo - Multiple Imputation (MCMC-MI)*

The method of handling missing efficacy data relative to the supportive hybrid estimands for the primary and secondary endpoints at Week 16 will be based on Markov Chain Monte Carlo Multiple Imputation (MCMC-MI). For patients who discontinue treatment due to lack of efficacy prior to Week 16, set to the patient’s baseline value subsequent to this time through Week 16. MCMC-MI will be used to handle the remaining missing data.

The method of handling missing efficacy data relative to the supportive hybrid estimand for secondary endpoints at Week 24 will be based on MCMC-MI. For patients who discontinue treatment due to lack of efficacy after Week 16, set to the patient’s baseline value subsequent to this time through Week 24. MCMC-MI will be used to handle the remaining missing data.

Imputation will be conducted within each treatment group independently so that the pattern of missing observations in one treatment group cannot influence missing value imputation in another.

For each imputation process, 25 datasets with imputations will be calculated. The initial seed values are given in Table KGBP.5.3. The response rates and their associated SEs will be computed for each data set using SAS PROC FREQ with the riskdiff option specified for the appropriate column in the TABLES statement. The response rates and SEs from the resulting output will be combined across the 25 imputed datasets using SAS PROC MIANALYZE.

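### The primary EASI-75 rate counts only participants still on treatment at Week 16, not all eligible participants as Protocol 6.3 states, and no planned analysis counts rescue as non-response by rule

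*Protocol*

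**What the plan says.** Protocol 6.3, on measures to minimize bias, states that "potential bias will be reduced by specifying treatment response ascertained from all eligible participants and safety reporting". The primary objective in Protocol 3 is to assess the drug's effect "in reducing the signs and symptoms of AD in participants with moderate-to-severe AD and skin of color", with no condition on remaining on treatment.

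The rules that decide who enters the primary rate are elsewhere:

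- Protocol 6.8.5 (and 6.8.4 in the same terms): "Participants that receive Rescue Therapy must be discontinued from the study".
- The primary estimand in Protocol 1.1 and 3, repeated in SAP 5.2.1, restricts the population to participants on treatment up to Week 16. It then says: "There are no intercurrent events for this population since participants who initiate rescue medication are discontinued from the study and hence study treatment".
- SAP Table KGBP.5.3 gives the primary analysis set as the part of the ITT population still on treatment, analysed as observed. SAP 5.4.1 explains that under this strategy "only data from completers at the visit are relevant", and acknowledges that ICH E9(R1) does not recommend it.
- SAP 5.2.2 adds two supportive ITT estimands for the primary endpoint. In Table KGBP.5.3 the hybrid estimand sets discontinuation for lack of efficacy to baseline. Discontinuation for every other reason, with rescue listed there by name, is set to missing and imputed by MCMC-MI. The hypothetical estimand sets all discontinuations to missing and uses LOCF.

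**The concern.** The bias statement in 6.3 and the primary analysis describe different groups. Rescue is provided for AD that has become intolerably worse, so leaving by that route is related to the outcome. Membership of the analysed group is settled after baseline and cannot be known at enrolment. There are no intercurrent events only because the population has been selected to contain none; the introduction to SAP 5.4 itself gives rescue treatment and treatment discontinuation as examples of such events.

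With no control arm and no blinding, the decision to start rescue also fixes the denominator. At stake is how the headline percentage will be read. It answers how many of those who stayed on treatment had responded, whereas the objective and 6.3 lead a reader to expect a rate among all eligible participants. The supportive analyses do not supply that rate with rescue counted as failure.

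**Working it through.** **Inputs.** From Protocol 9.5: anticipated EASI-75 rate about 50%; precision stated for 80 enrolled; about 95 to be enrolled; two-sided 90% Wilson intervals. The number leaving before Week 16 is not given. Protocol 7.2 says only that discontinuation should be rare. The exit counts and failure shares below are therefore assumptions.

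**1. The plan's own figure.** With z = 1.645, the Wilson half-width at p = 0.5 is z/(1 + z²/n) × √(0.25/n + z²/(4n²)). At n = 80 it is 9.04 points, so the interval is 40.96% to 59.04%, as tabulated. All seven tabulated intervals reproduce. At n = 95 the half-width is 8.3 points.

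**2. Against an all-enrolled rate with exits as non-response.** Let N be the number enrolled, L the exits before Week 16, and R the responders on treatment at Week 16. For simplicity every stayer is assessed at Week 16.

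- As observed: R/(N − L)
- All enrolled, composite: R/N

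The numerators are the same and N − L ≤ N, so the as-observed rate is never lower, and it is higher whenever anyone leaves (and R > 0). With N = 95 and R = 48, the composite rate is 48/95 = 50.5%:

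| Exits | Analysed | As observed | Excess (points) |
|---|---|---|---|
| 5 | 90 | 48/90 = 53.3% | 2.8 |
| 10 | 85 | 48/85 = 56.5% | 5.9 |
| 14 | 81 | 48/81 = 59.3% | 8.7 |
| 19 | 76 | 48/76 = 63.2% | 12.6 |

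From 14 exits the excess is larger than the 8.3-point half-width at n = 95.

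**3. Against what leavers would have shown.** Now let R include the r leavers who would have responded. The as-observed rate is (R − r)/(N − L), and the comparison is R/N. With N = 95, R = 48 and 10 exits:

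- 75% of leavers failing: r = 2.5, so 45.5/85 = 53.5%, an excess of 3.0 points.
- 50% failing: r = 5, so 43/85 = 50.6%, an excess of about 0.

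The sign can reverse. With R = 38 (40.0%), 10 exits and half of them failing, the rate is 33/85 = 38.8%, which is 1.2 points too low. The one-way result in step 2 therefore holds against the composite rate, not against this counterfactual.

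**4. What each planned analysis does with a rescue exit before Week 16** (SAP Table KGBP.5.3, 5.4.2, 5.4.3).

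- Primary: left out of the rate.
- Hybrid: set to missing, then MCMC-MI, so the imputed value may be a response.
- Hypothetical: set to missing, then LOCF, so the result depends on the last EASI recorded.

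None assigns non-response by rule.

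**The case against.** The best defence is that nothing is hidden. The question, population and analysis all state the on-treatment restriction, and amendment b aligned them on purpose. No hypothesis is tested, and the intervals are given as reference only. This stands: a reader might infer that the primary rate is biased for its own estimand, and it is not.

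It is also fair that 6.3 should not be read as the sole protection against bias. The same section adds "Adherence to the study design requirements, including those specified in the SoA, is essential and required for study conduct" and has sites submit IGA/EASI results through the IWRS. Section 8.1.1 adds "Assessors must be trained and certified by the sponsor prior to conducting this assessment", with one assessor per participant where possible. The sentence at issue is, however, the only one of these measures that concerns whose response is counted.

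A third argument is that response can be ascertained in leavers even if they are not in the rate. Under Protocol 7.1, after stopping the drug "the participant will remain in the study to complete procedures for an early discontinuation visit and post-treatment follow-up", and the Schedule of Activities has EASI at the early discontinuation visit. That is true of data collection, but the primary analysis does not use those values as Week 16 outcomes.

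A fourth is that ITT analyses are planned, and that disposition by reason and rescue use will be tabulated on ITT. A reader might infer from this point that no ITT rate exists; that would be wrong. In practice LOCF would probably carry forward non-response for someone worsening into rescue (an inference). Those analyses still leave rescue without a non-response rule.

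Finally, exits may be few. Permitted topical treatment is broad, and discontinuation for adverse events was 1.4% on lebrikizumab in the two monotherapy Phase 3 trials (Protocol 2.3). That figure does not cover rescue or other exits. If exits are few, the fix changes the rate little.

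**Conclusion.** The point holds in this form. Section 6.3 and the primary objective describe response in all eligible participants; the primary rate describes participants who stayed on treatment; and no planned analysis counts rescue as non-response by rule. Relative to an all-enrolled composite rate the direction is certain. The size is not: in the illustration it runs from 2.8 points at 5 exits to 12.6 at 19, on assumed exit counts. Relative to what leavers would have shown, it may be about 3 points, nil or slightly negative at 10 exits, depending on who leaves.

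Two further readings are not supported. A reader might infer a known upward bias of a given size, but the documents give no rescue or dropout rate, and leavers for reasons unrelated to AD may have responded. A reader might also infer that the planned precision is lost because it is stated per enrolled participant. The 10-point Wilson half-width still holds with about 65 analysed, that is, after about 30 exits from 95. The issue is the level and meaning of the rate, not its precision. The change should be made, though the declared analysis is not invalid on its own terms.

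**What to change.** Make the primary Week 16 EASI-75 rate an all-enrolled (ITT) rate, with rescue or permanent discontinuation before Week 16 counted as non-response (composite strategy). State separately how a missed Week 16 assessment in someone still on treatment is handled; the MCMC-MI already specified could serve. Keep the as-observed rate as supportive, labelled as applying to participants still on treatment. Align the clinical question and Population attribute in Protocol 1.1, 3 and 9.3.2 and SAP 5.2.1, so that 6.3 describes the primary analysis.

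At minimum, move rescue in Table KGBP.5.3 from the set-to-missing column to the composite non-response column of the hybrid estimand.

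Two pairs of passages must also be reconciled:

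- Protocol 6.8.4 and 6.8.5, which discontinue rescue users from the study, with 7.1, which lists rescue as a reason to stop study intervention while the participant stays for the early discontinuation visit and follow-up.
- Protocol 9.3.2, which includes everything observed, with SAP 5.4.1, which uses completers at the visit.

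The cost is a protocol and SAP amendment and one further table, with no new data collection. Amendment b, which last changed this estimand, was classed as substantial, so this is more than an editorial change. The primary percentage will be somewhat lower, and exits unrelated to AD will be counted conservatively.
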